8.3 Number of Subjects

A previous study by Zeng et al. found that the rate of any level of eyelid erythema when using 3M Medipore is 50% while when using 3M Kind Removal Silicone Tape is 33%. We will assume that the rate of erythema with 3M Tegaderm may be similar to that of 3M Medipore and the rate of erythema with EyeGard may be similar to that of 3M Kind Removal Silicone Tape. Given that we are doing a study of matched pairs of subjects (the same study subject will undergo both treatments, one on each eye), the McNemar test is most appropriate. In order to detect a difference in erythema rates with an alpha of 0.05 and 80% power, G*Power determined that the total sample size needs to be 288 eyes, which is 144 patients. In order to account for a 10% attrition rate, we will plan on recruiting 159 study subjects.

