2.1 Background and Rationale

In the 1980s, taping eyes shut during anesthesia became a common practice due to the recognition of corneal abrasions as a risk of anesthesia (1). However, there is no single accepted practice of how to protect the eyes during anesthesia, and a variety of different tapes and techniques have been adopted in different institutions.

While the risk of corneal abrasion significantly decreases with the use of eye tape, patients may occasionally experience eyelid irritation from the adhesive. While the eyelid irritation is generally limited to mild erythema that resolves on its own within a day or two of receiving anesthesia, the irritation may affect patient satisfaction (2).

At Tufts Medical Center, a variety of adhesive tapes are used to shut the eyes during anesthesia, including 3M™ Tegaderm™ and the Sharn Anesthesia EyeGard®, with no preference for one or the other. While all of these products decrease the risk of corneal abrasion, none of these products have been shown to be superior to the others in terms of eyelid irritation. According to Sharn Anesthesia, “The [EyeGard®] adhesive is light enough to reduce damage to the outer eye” (3). However, there is no scientific evidence to support this claim. All we know is that the EyeGard is coated with a medical grade, pressure-sensitive acrylic adhesive and that there are no phthalates, it is latex free and silicone free.

The purpose of this study is to compare the rate of eyelid erythema after anesthesia with the use of Tegaderm™ vs. the EyeGard®. Our hypothesis is that there will be a difference in the rate of erythema between the two groups.

- Is there an active control group?

Yes No

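### Section 8.3 multiplies 144 by 1.10 instead of dividing by 0.90, so 159 patients leave 143 after the stated 10% attrition; the paired assumption behind 144 should be stated in the same edit

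*Combined protocol and SAP*

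**What the plan says.** Section 8.3 (Number of Subjects) takes erythema rates from an earlier tape study, one for each tape: "the rate of any level of eyelid erythema when using 3M Medipore is 50" (percent), and "while when using 3M Kind Removal Silicone Tape is 33" (percent). It carries these over to Tegaderm and EyeGard respectively. It chooses the McNemar test because "the same study subject will undergo both treatments, one on each eye".

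The target is set "with an alpha of 0.05 and 80% power", and the result is reported as: "G*Power determined that the total sample size needs to be 288 eyes, which is 144 patients". The allowance for loss follows: "In order to account for a 10% attrition rate, we will plan on recruiting 159 study subjects".

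The section gives no discordant proportion, odds ratio or within-patient correlation, and does not say whether alpha is one-sided or two-sided. Section 2.1 states a non-directional hypothesis: "Our hypothesis is that there will be a difference in the rate of erythema between the two groups".

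Section 5.1 (Study Timelines) also plans 159 subjects in total. The study schema ahead of section 2 shows 159 patients in each of two arms.

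**The concern.** An allowance for attrition should leave the required number after the stated loss. The recruitment figure here does not: the margin was taken as 10% of the number needed, whereas the loss will be 10% of the number recruited. The enrolment target therefore misses its own stated allowance.

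The same paragraph also leaves out an input to the power claim. The McNemar test uses only patients whose two eyelids differ. Two marginal rates do not say how many such patients there will be, so a reader cannot reproduce 144 or judge the 80% without supplying an assumption. At stake are a correct enrolment target and a sample-size statement that can be checked.

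**Working it through.** **Inputs.** All come from section 8.3 unless noted: p1 = 0.50 (Tegaderm), p2 = 0.33 (EyeGard), alpha 0.05, power 80%, 144 patients needed, 10% attrition, 159 recruited. Two-sided testing is inferred from the hypothesis in section 2.1.

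**1. Reproducing 144.** Assume the two eyelids of a patient are uncorrelated:

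- Tegaderm eyelid only: 0.50 × (1 − 0.33) = 0.335
- EyeGard eyelid only: 0.33 × (1 − 0.50) = 0.165
- Discordant proportion: 0.335 + 0.165 = 0.50; odds ratio 0.335 / 0.165 = 2.03

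The power of the exact two-sided McNemar test, summed over the possible numbers of discordant pairs, is 79.9% at 142 pairs, 80.2% at 143 and 80.4% at 144. The smallest number reaching 80% is 143, so 144 is reproduced to within one pair. A one-sided exact test would need 115, and the large-sample two-sided formula gives 134, so 144 fits the two-sided exact test better than either.

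A two-sided Fisher exact test on two independent groups at the same rates gives 79.9% at 143 per group and 80.4% at 144 per group, that is, 288 in total. Two different routes therefore lead to the plan's figure or within one pair of it.

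**2. The attrition step.**

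- Plan's route: 144 × 1.10 = 158.4, rounded up to 159
- What remains: 159 × (1 − 0.10) = 143.1, that is, 143
- Number that keeps 144: 144 / (1 − 0.10) = 160; check 160 × 0.90 = 144
- Attrition that 159 covers: 1 − 144/159 = 15/159 = 9.4%

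Power cost with uncorrelated eyelids: 80.4% at 144 against 80.2% at 143.

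**3. How far the unstated assumption matters.** Hold 50% and 33% fixed and let phi be the within-patient correlation:

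- Both eyelids: p11 = p1·p2 + phi × √[p1(1 − p1)·p2(1 − p2)] = 0.165 + 0.235 × phi
- Discordant proportion: (p1 − p11) + (p2 − p11) = 0.83 − 2·p11

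The documents give no phi, so the values below are an assumed range.

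| phi | Discordant proportion | Exact power at 144 pairs | Pairs for 80% |
|---|---|---|---|
| −0.1 | 0.547 | 76.3% | 157 |
| 0 | 0.500 | 80.4% | 143 |
| 0.2 | 0.406 | 88.5% | 116 |
| 0.3 | 0.359 | 92.4% | 104 |
| 0.5 | 0.265 | 98.3% | 75 |

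**4. The recruitment totals.** The schema's two arms of 159 add to 318 patients, against 159 in sections 5.1 and 8.3. Since 318 is also the number of eyes in 159 patients, the schema may be counting eyes, but the documents do not say so.

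**The case against.** The strongest reply is that nothing of consequence follows from the attrition slip. Under the assumption that reproduces 144, 143 pairs already reach 80%, so 159 less 10% still delivers the stated power. The primary photograph is taken on day 1, so a patient lost before the day 2 survey is lost to satisfaction but not to erythema. If the schema's 318 were the true target, 318 × 0.90 = 286.2 would far exceed 144. All of this stands as to size. It does not make 159 the right figure for a 10% allowance on 144, and the conflict with the schema is a further reason to edit the recruitment number.

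Two stronger readings are tempting. A reader might infer that the 80% is at risk unless the two eyelids are uncorrelated. The table shows otherwise: with the marginal rates fixed, power is at least 80% at zero and at every positive correlation shown, and drops below only when the correlation is negative. The documents give no reason to expect a negative one, since both eyelids share the same skin and the same anesthetic.

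A reader might also infer that the calculation ignored the pairing, because an unpaired Fisher test gives exactly 288. The documents do not show which G*Power procedure was run. An exact McNemar calculation with uncorrelated eyelids, which is a paired calculation, comes within one pair of the same figure. Agreement with both routes cannot identify the one used.

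**Conclusion.** The attrition arithmetic is wrong as written: 159 leaves 143, one short of the stated 144, and covers 9.4% loss, not 10%. The effect is about 0.3 percentage points of power, which is negligible. This rests only on the plan's own figures, plus uncorrelated eyelids and a two-sided exact test for the power values.

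The absent discordant proportion and sidedness are a reporting gap and not evidence of low power. The figure of 144 is consistent with a discordant proportion of 0.50 and a two-sided test. Depending on the true correlation, power at 144 pairs would run from about 76% (phi −0.1) to about 98% (phi 0.5). The zero-correlation assumption is therefore conservative if a patient's eyelids tend to respond alike. The point is minor and worth correcting because it costs almost nothing.

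**What to change.** 1. In section 8.3, either keep 159 and say that it allows for 9.4% attrition, or state 160 (144 / 0.90). If 160 is chosen, change section 5.1 to match.
2. Reconcile the schema's 159 per arm with the total in sections 5.1 and 8.3.
3. In section 8.3, state the procedure, discordant proportion (or odds ratio) and sidedness actually entered in G*Power. If no discordant proportion was entered, say so and give one that can be justified. If zero correlation is adopted, describe 80% as the power under that assumption, and show results for both positive and negative correlation, not only the favourable side.

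The cost is two or three sentences, a corrected schema and at most one more patient than the 159 in section 8.3.

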8.4 Data Management

The data to be collected will be divided into two general groups: (1) Paper forms, such as the consent forms and data collection sheets, will be stored in the principal investigator's locked office. (2) Digital form, such as the data collection excel spreadsheet which includes the following variables: Subject ID, R and L eye tape assignments, length of surgery, R and L eye pre-op photo numbers, R and L eye pre-op scores (from three dermatologists), R and L eye post-op photo numbers, R and L eye post-op scores (from three dermatologists), final erythema score (post minus pre), patient satisfaction with R eyelid condition, patient satisfaction with L eye condition, and additional notes, will be stored on a Tufts Medical Center provided, password protected, encrypted, Box storage account, which is compliant with institutional policies regarding HIPAA and the IT department. (3) All photos will also be stored on Box.com.

8.5 Randomization

Will subjects be randomized?

Yes No

In order to randomly allocate study subjects to one of three arms entirely by chance, we will use the on-line randomization tool "Research Randomizer Version 4.0, www.randomizer.org," which is a computer-based "random number generators," the numbers are generated by use of a complex algorithm (seeded by the computer's clock) that gives the appearance of randomness. This tool has been studied and validated as an adequate randomization tool, to generate a randomization list. Allocation concealment will be maintained by preparing sequentially numbered, sealed, opaque envelopes, which will contain the randomization assignment consistent with the generated randomization list.

The following strategies will be implemented in order to ensure blinding:

- (a) When a subject enrolls in the study, the co-investigator, [name], will open the envelope with randomization number inside. [name] will be the one to apply and remove the tapes. Once the tapes are removed, a second set of photographs will be taken. The dermatologists who will be in charge of determining the primary outcome (erythema score) will not be present during any part of the procedure.
- (b) The photos will only be linked to the experimental variable (tape type) by the data collection spreadsheet that is only accessible to the principal investigator, [name], and the co-investigator, [name]. After data collection for the study is complete, the photos will be presented to the dermatologists independently in a blinded manner.
- (c) Each dermatologist's grading will subsequently be recorded in the data collection spreadsheet by the co-investigator. Therefore, the dermatologist will have no opportunity to determine the type of tape used at any point during the study.
- (d) Study subjects will not be informed of which tape is assigned to which eyes, and the tape will be applied and removed while the patient is under anesthesia. Therefore, the patient will be blind to the type of tape used throughout the course of the study, including when he/she is reporting his/her satisfaction with post-operative eyelid condition.

9 Drugs or Devices

Will the research involve drugs?

Yes No

Will the research involve devices?

Yes No

10 Study Administration

10.1 Setting

Tufts Medical Center will be the sole research site. TegadermTM and EyeGard® tapes will be administered in the operating room per routine clinical care. Patients will then be followed in the recovery room until post-operative day 1.

10.2 Registration

The co-investigator, [name], will ensure the eligibility of subjects and obtain their informed consent before implementing any study related interventions.

10.4 IRB Review

An appropriate IRB registered with the OHRP, will review and approve this study. Any amendments to the protocol or informed consent documents will be reviewed and approved by the IRB prior to use, unless required to eliminate an apparent immediate hazard to subjects.

10.5 Multi-Site Research

Is this a multi-site study where Tufts is the sponsor, primary grant recipient, or coordinating site?:

Yes No

10.6 Community-Based Participatory Research

Will this study involve community-based participatory research?

Yes No

